#### **Exclusion Criteria**

- Primary or secondary progressive MS at time of enrollment
- Patients who are not eligible to receive MRI

## **Data Source/Data Collection Process**

Three types of data will be collected in the study

- 1. clinical status, such as therapy change and relapse activity
- 2. clinical scores, such as EDSS
- 3. imaging data (brain MRI) using a standardized image acquisition protocol including a high-resolution T1w-MRI.

#### Study procedures

• Expanded Disability Status Scale (EDSS) examination

The EDSS is a standardized, widely accepted, numerical scale method used to evaluate disability in people with MS (Kurtzke 1983). The EDSS is evaluated according to signs and symptoms observed during a standard neurological examination. Based on a neurological examination, 8 functional systems (visual, brain stem, pyramidal, cerebellar, sensory, bowel & bladder, cerebral, and other functions) are scored from 0 (no disability) to 5 or 6 (more severe disability). Ambulation is assessed based on distance the patient is able to walk, whether assistance is required, or restrictions are present. The EDSS score ranges from 0 (normal) to 10 (death due to MS) in 0.5 unit increments. A template or an adaptation of this template, which can be found in the appendix, shall be used for documentation. The study will require the same evaluator to perform all EDSS assessments for an individual patient when possible. In addition, EDSS raters will be certified using the Neurostatus Standardized Examination and Assessment (www.neurostatus.net/training) prior to study initiation and examiners will be recertified every two years throughout the conduct of the study.

#### • Relapse activity assessment

A relapse is defined as the occurrence of new or worsening neurological symptoms attributable to MS and immediately preceded by a relatively stable or improving neurological state of at least 30 days. The new or worsening neurological symptoms must be accompanied by objective neurological worsening consistent with an increase of at least half a point on the EDSS, or 2 points on one of the appropriate FS scores, or 1 point on two or more of the appropriate FS scores. The change must be documented by the evaluator at either scheduled or unscheduled visits and must affect the FS scales that correspond to the

patient's symptoms (e.g., pyramidal, gait, cerebellar, brainstem, sensory, or visual). Symptoms must persist for > 24 hours and should not be attributable to confounding clinical factors (e.g. fever, infection, injury, adverse reactions to concomitant medications).

#### • Brain MRI examination

Brain MRIs will be acquired using a standardized image acquisition protocol including high-resolution T1w-MRIs. Standardized means that the protocol complies with the recently published 2021 MAGNIMS-CMSC-NAIMS consensus recommendations on the use of MRI in patients with MS (Wattjes et al. 2021). Gadolinium is administered depending on the judgement of the physician or radiologist. The same or a similar brain MRI protocol will be used across all sites. All participating radiology centers have to go through a protocol qualification procedure orchestrated by the investigator. The qualification status is continuously monitored by the investigator.

#### Time and events schedule

| Event  | Enrollment /
baseline visit
(V1) | Additional visits to the study center | Follow-up: 2nd
visit (V2) | Follow-up: 3rd
visit (V3) | Follow-up: 4th
visit (V4)
(extension) |
|--|--|---------------------------------------|------------------------------|------------------------------|---|
| Time [first
patient in - last
patient out] | 0 - 9                                  | Approx. every 6 months                | 12 – 21                      | 24 - 33                      | 36 - 45                                     |
| Documentation
of medical
history           | X                                      |                                       |                              |                              |   |
| Assessment of inclusion and exclusion parameters | X                                      |                                       |                              |                              |   |
| Assessment of clinical status                    | X                                      | Х                                     |                              |                              |   |
| EDSS   | X                                      | X                                     |                              |                              |   |
| Brain MRI examination(1)                         | X                                      |                                       | X                            | X                            | X   |

 There is no strict requirement that brain MRI examination shall fall within +/- 3 months of the assessment of clinical scores.

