## **Secondary Objectives**

- (S1) To demonstrate that worsening of MS-related disability is associated with loss of thalamus volume when loss of whole brain volume is within the normal range.
- (S2) To demonstrate the change of thalamus volume during 24 months is predictive of the change of disability during the following 12 months (months 24-36).

[figure not shown]

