## Length of follow-up.

The prospective observational study runs for 24 months plus the additional 9 months enrollment period. In total a baseline visit (V1) and two follow-up visits (V2 and V3) per study subject are planned. The main purpose of these visits is to prescribe and schedule a brain MRI examination with the affiliated radiology center. It is important that brain MRIs are performed annually with a minimum of 11 months apart. If the decision is made to extend the study for another 12 months the individual study subject will be followed for 36 months adding another visit (V4) to the study schedule.

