#### Secondary hypotheses and secondary endpoints

(S1) Worsening of MS-related disability is associated with loss of thalamus volume also if loss of whole brain volume is within the normal range.

Patients will be dichotomized with respect to the annual EDSS change during 24 months ('stable disability' versus 'progression of disability'), with respect to the annual change of thalamus volume ('stable thalamus volume' versus 'decline of thalamus volume'), and with respect to the annual change of brain parenchymal volume ('stable parenchymal volume' versus 'decline of parenchymal volume'). The parenchymal volume will be determined from the same T1w-MRI as the thalamus volume using a deep-learning based method developed and validated by JDX. The annual change of the parenchymal volume will be computed by linear regression of parenchymal volume versus time. Predefined cutoffs will be used for dichtomization. The association between dichotomized disability change and dichotomized thalamus volume change will be tested in the subgroup of patients with stable parenchymal volume using the chi-square statistic.

(S2) The change of thalamus volume during 24 months is predictive of the change of disability during the following 12 months (months 24-36).

EDSS will be determined at additional visits at 30 and 36 months. The annual change of EDSS between months 24 and 36 will be determined by linear regression of EDSS versus time including 24, 30 and 36 months. The annual change of EDSS between months 24 and 36 will be dichotomized using a predefined cutoff. The association between dichotomized disability change between 24 and 36 months and dichotomized thalamus volume change between baseline and 24 months will be tested using the chi-square statistic.

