# Primary objective: To demonstrate that the change of MS-related disability during a period of 24 months is inversely associated with change of thalamus volume during the same period.

In a previous project sponsored by Celgene, the investigators in this study developed and validated a technique that allows reliable and robust calculation of change in regional volumes based on a longitudinal approach in high-resolution T1w MRIs (Opfer et al. 2020). Such an approach allows percentage estimation of volume change of corresponding regions in successive high-resolution T1w MRIs and is much less susceptible to noise than conventional methods based on calculation of absolute volumes at different time points and a regression model to estimate volume change. It has the potential to overcome the technological limitations that hindered the work of Eshaghi et al. (2018).

[figure not shown]

Figure 3. Linear regression of all EDSS measurements

With this approach, it is methodologically feasible to assess TVL and deep GMVL for individual MS patients.

MS-related disability will be characterized by the Expanded Disability Status Scale (EDSS). The EDSS will be determined at inclusion (baseline), at 24 months after inclusion, and at additional visits at time intervals approx. every 6 months in between. The annual change of EDSS during the 24 months' period will be computed by linear regression of EDSS versus time including all visits (Fig. 3). The slope of the regression line will be the annual change of EDSS.

[figure not shown]
For the correlation analysis annual change of EDSS and annualized TVL will be considered as continuous variables. For all study subjects three high-resolution T1w-MRI scans will available. TVL will be calculated for each pair of two consecutive MRI scans. Annualized TVL between the baseline (BL) and last follow-up (FU) scan will be calculated by multiplying the TVL between the two consecutive scans and dividing the resulting TVL with the time interval between BL and FU scan.

A Pearson correlation analysis will be used to test for with a significance level of p = 0.05. Outcomes can be modelled both as dichotomous (CDP – yes, no) and continuous (raw EDSS score) variables. In case of dichotomous variables, a logistic regression will be used.

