# (S2) To demonstrate that the change of thalamus volume during 24 months is predictive of the change of disability during the following 12 months (months 24-36).

We will build a statistical model based on clinical and MRI (estimated from three MRI measurements sampled at baseline (BL), at month 12 and at month 24) parameters to predict disability progression between month 24 and month 36. EDSS will be determined at additional visits at 30 and 36 months. The annual change of EDSS between months 24 and 36 will be determined by linear regression of EDSS versus time including 24, 30 and 36 months. The annual change of EDSS between months 24 and 36 will be dichotomized using the same predefined cutoff as deployed for (S1) (see above). The association between dichotomized disability change between 24 and 36 months and baseline (BL) parameters and TVL between baseline and 24 months will be tested using the chi-square statistic.

The following parameters will be used:

- Clinical scores / characteristics @ BL:
  - Age and sex

\_

<sup>1 Guideline on clinical investigation of medicinal products for the treatment of Multiple Sclerosis from EMA as of 26 March 2015

- disease duration (DD)
- EDSS
- Therapy
- MRI @ BL
  - z-scores of thalamus and whole brain volume
  - T2 lesion load
- MRI @ BL, month 12 and month 24
  - TVL and BVL

The model will be based on multivariate regression or support vector machines. The performance of the model will be characterized using a receiver operating characteristic (ROC) curve. The ROC will be evaluated with respect to accuracy, area under curve (AUC), sensitivity (true positive rate) and specificity (true negative rate). Within each classifier including both clinical and neuroradiological features, permutation importance will be calculated for each feature and for the random variable: only parameters whose importance are higher than the random variable's importance, will be considered as relevant in the classifier.

Baseline volumes for thalamus and whole brain will be estimated using a novel convolutional neural network-based approach, recently submitted for publication (Opfer et al. 2021).

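### A V3 scan taken after the month-24 EDSS puts part of the S2 predictor inside its outcome window, and the protocol sets no S2 limit on that scan's date

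*Protocol*

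**What the plan says.** The S2 hypothesis in Protocol section 3 (Secondary hypotheses and secondary endpoints) reads "The change of thalamus volume during 24 months is predictive of the change of disability during the following 12 months (months 24-36"). Section 4, under S2, gives the nominal scan times, "three MRI measurements sampled at baseline (BL), at month 12 and at month 24", and the outcome, an annual EDSS change "determined by linear regression of EDSS versus time including 24, 30 and 36 months".

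Other parts of the Protocol govern when the scans happen and how they are used:

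- Length of follow-up: "It is important that brain MRIs are performed annually with a minimum of 11 months apart". This is a floor. No maximum and no tolerance around month 24 is given.
- The same section, on the visits: "The main purpose of these visits is to prescribe and schedule a brain MRI examination with the affiliated radiology center".
- Time and events schedule, footnote 1: "There is no strict requirement that brain MRI examination shall fall within +/- 3 months of the assessment of clinical scores".
- Section 4, primary objective (repeated under Missing data handling): TVL from baseline to the last follow-up scan is annualised by "dividing the resulting TVL with the time interval between BL and FU scan". Nothing cuts the interval at month 24.
- Section 5, Bias/confounding: the only timing rule for discarding MRI data concerns a therapy switch less than 6 months before the scan.

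The schedule's 24-33 entry for V3 stands in a row labelled first patient in to last patient out. It reflects the 9-month enrolment and is not a window for the individual patient.

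**The concern.** S2 differs from the primary objective only in temporal order. The primary objective asks whether thalamic loss and EDSS change go together in the same period. S2 asks whether loss in one period forecasts disability change in the next, which requires the TVL interval to end before the EDSS window begins.

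The protocol's scan rules do not secure that. If V3 is scanned some months after the month-24 EDSS, the TVL interval runs into the outcome window, which does not move. Volume loss in the overlap may accompany EDSS change in the same months. Part of the same-period association then enters S2 and would be reported as prediction. Because the scan is arranged at the visit, some scans after month 24 are to be expected.

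**Working it through.** **1. The plan's own figures.** For S2, section 4 assumes 0% versus 5% progression, type I error 0.05 and type II error 0.20. The two-sided formula with pooled variance and no continuity correction gives

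n = [1.96·√(2·0.025·0.975) + 0.8416·√(0.05·0.95)]² / 0.05² = (0.4327 + 0.1834)² / 0.0025 ≈ 151.9, so 152 per group and 304 in total, as stated.

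The primary sample size also reproduces: [(1.96 + 0.8416) / atanh(0.15)]² + 3 ≈ 346.6, so 347. So does the attrition figure: 600 × 0.85³ = 368. None of these is in dispute; the point is about timing.

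**2. Overlap.** Let the V3 scan fall d months after month 24, with the baseline scan at month 0. The protocol gives no value for d, so these are assumptions.

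| d (months) | share of TVL interval, d/(24+d) | share of outcome window, d/12 |
|---|---|---|
| 1 | 4% | 8% |
| 3 | 11% | 25% |
| 4 | 14% | 33% |
| 6 | 20% | 50% |
| 9 | 27% | 75% |

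**3. Size of the leak.** Assumptions:

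- no true prediction: thalamic change before month 24 is unrelated to EDSS change after it;
- increments independent over time;
- same-period correlation 0.15, the protocol's figure for the primary objective;
- every V3 scan late by the same d;
- both variables continuous, although the protocol's S2 test is a chi-square on dichotomised EDSS change.

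For EDSS values at exactly 24, 30 and 36 months, the least-squares slope equals the month-36 value minus the month-24 value, per year, so treating the outcome as change over 12 months is fair. The covariance comes only from the d shared months:

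r(d) = 0.15·d / √[(24 + d)·12]

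The chance of a significant result at two-sided 0.05 is Φ(m − 1.96) + Φ(−m − 1.96), with m = atanh(r)·√(N − 3) and N = 304.

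| d (months) | r(d) | false-positive rate |
|---|---|---|
| 1 | 0.009 | about 5% |
| 3 | 0.025 | about 7% |
| 4 | 0.033 | about 9% |
| 6 | 0.047 | about 13% |
| 9 | 0.068 | about 22% |

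Worked case, d = 4: r = 0.6/√336 = 0.0327; m = 0.0327 × √301 = 0.568; Φ(−1.392) + Φ(−2.528) = 0.082 + 0.006 = 0.088.

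At the expected 368 patients the rates for 3 and 6 months are about 8% and 15%. All are lower if only some patients are late.

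**4. How late is plausible?** Enrolment runs from +3 to +12 months after launch. Milestone M-12 wants V3 done for more than about 350 patients by +36, and the attrition table expects 433 at month 24. With uniform enrolment and a common delay d, the number done by +36 is 433 × (9 − d)/9. This reaches 350 only if d is about 1.7 months or less; at d = 4 it is about 240. A long delay therefore cannot be the general pattern if M-12 is met. M-12 does not bind the individual: a patient enrolled at +3 could be scanned at month 33 and still count.

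**The case against.** The strongest reply is that the S2 text already defines the predictor as TVL from baseline to month 24, with annual scans at months 0, 12 and 24. Only a tolerance is missing, and analysis windows are commonly left to a statistical analysis plan. The footnote suits a non-interventional study in which no procedure is mandatory. M-12 limits typical delays, the 11-month floor also allows early scans (22 months after baseline after two intervals), and an early scan does not disturb the order. The distortion is small up to about 3 months. S2 is also a secondary objective in a conditional extension.

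Most of this stands and limits the size of the point. It does not remove it. The protocol does more than leave a window unwritten: it expressly waives closeness between scan and clinical scores, runs TVL to the actual last scan and fixes the EDSS window. Together these work against the order that S2 claims. The waiver may be tolerable for the same-period primary analysis.

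A reader might go further in three ways that the documents do not support:

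- **Scan dates have no practical limit.** The nominal times and M-12 argue against this as a general pattern.
- **Nothing ties the EDSS to month 24**, because the schedule ticks no EDSS under V3. The study design, primary endpoint and S2 texts all fix an EDSS at 24 months, and the column for visits about every 6 months can hold it.
- **Delays can only accumulate.** The scan is arranged at the visit, which makes lateness likely, but the spacing rule also permits early scans.

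**Conclusion.** The point holds in a limited form. For a patient whose V3 scan falls after the month-24 EDSS, part of the S2 predictor is measured inside the outcome window, and no rule in the protocol prevents or handles this. It would be too strong to infer that S2 as a whole is not a prediction: patients scanned on time are unaffected, and for late ones the association is mixed with some same-period change.

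Under the assumptions above, with every scan late, the false-positive rate is about 7%, 9% and 13% at 3, 4 and 6 months instead of 5%. The true inflation depends on the share of late scans and the length of delay, which the document does not give. The effect on the dichotomised chi-square test and on the ROC performance of the S2 model was not calculated. The primary objective and S1 do not need this ordering. The point should be corrected before the S2 analysis, but it does not threaten the study.

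**What to change.** In the S2 text of section 3 (Secondary hypotheses and secondary endpoints) and section 4, state that footnote 1 of the schedule does not apply to S2. Base the S2 analysis on patients whose V3 scan is on or before the month-24 EDSS or within a short prespecified tolerance, for example 1 month, where the illustration shows almost no inflation. Report S2 with all V3 scans as a sensitivity analysis. At the least, keep all scans in the main analysis and add a sensitivity analysis that excludes late ones.

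The cost is protocol wording and some S2 patients. Scan and EDSS times are already needed for the annualisation and the regression, no visit is added and nothing becomes mandatory. If 600 are enrolled and dropout is 15% a year, 368 are expected at month 36 against 304 required, so 64 (64/368 = 17%) could be set aside before the total falls below the requirement. At the table's minimum enrolment of about 496 there is no such margin.

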#### Data entry and coding procedures

Together with information on the study, eligible patients will be informed about data capture, transmission and analyses processes. Once a patient is eligible and has given his/her informed consent to study participation and data collection, the evaluator will assign the patient a unique patient identification code which is always noted on the CRF. The code comprises the

identification number of the study center, the initials of the patient's name and the month and year of the patient's birthday. After each visit evaluators in the participating study centers will initially collect and document all necessary clinical data in due time on paper-based CRFs. CRFs are emailed or faxed to a centralized location of the investigator where trained members of the study team transcribe or transform the information on the CRFs to a central database. Patient data will be recorded in pseudonymized form (i.e. without reference to the patient's name) using exclusively the patient's identification code. Affiliated radiology centers transfer imaging data of study subjects via a secure data transfer service to the investigator. Prior to transfer of the imaging data to the investigator via an upload mechanism provided by the investigator, imaging data will be automatically pseudonymized.

For phase IV clinical trials (post-marketing) and the collection of patient data as part of routine clinical practice, the investigator can rely on an established infrastructure and a dense network of study centers and affiliated radiology centers. The processes and procedures are well established and have been supported by large Germany-wide research projects such as QUANTUM, PANGAEA and MAGNON since 2015. Meanwhile, a solid connection between radiology centers, neurology centers and the investigator has developed. Through this network, thousands of MS patients in Germany recently received standardized MRI procedures for disease and therapy monitoring in routine clinical practice, providing hundreds of neurological centers in Germany with regular quantitative information on brain volume loss and lesion activity.

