#### **Data Collection Methods:**

Three types of data will be collected: (1) clinical status, such as therapy change and relapse activity, (2) clinical scores, such as EDSS, and brain MRIs using a standardized protocol including a high-resolution T1w-MRI, at 20 study centers (neurology centers) and affiliated radiology centers in Germany. No procedures are mandatory, and no additional procedures are required beyond the standard examination of MS patients in routine clinical practice (standard-of-care). The EDSS will be assessed in a standardized manner. Evaluators at the study sites record clinical data and information required for the study after each patient visit and enter it into case report forms that are provided by the investigator. Affiliated radiology centers perform brain MRI scans according to standardized protocols, implemented together with the investigator, and transmit the image data to the investigator. Data privacy and security are ensured. Patient data are pseudonymized. The investigator can rely on an established infrastructure and a dense network of study centers and affiliated radiology centers. The processes and procedures are embedded in the clinical routine and have been successfully practiced since 2015.

Date: 23-Dec-2021 (revised 18-Feb 2022)

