## **Study Rationale**

The clinical course of multiple sclerosis (MS) is heterogeneous between patients and as of yet largely unpredictable on the single subject level. In addition to inflammatory demyelination and astrogliosis, neurodegeneration – a term that refers to structural axonal and neuronal damage plays a crucial role in the accrual of disability over time. An increasing body of evidence suggests that whole brain volume loss is indicative of disability progression (Sastre-Garriga et al. 2020). The mounting evidence prompted the MS community to add whole brain volume loss as a marker of tissue damage to the no-evidence-of-disease-activity (NEDA) concept. Since 2015 Germany-wide projects, such as QUANTUM, PANGAEA, MAGNON, have helped to establish a network of radiologists and neurologists for which accurate measurement and usage of whole brain volume loss (BVL) has become a "de-facto standard-of-care" (Schuh et al. 2020). Meanwhile, a solid connection between radiology centers, neurology centers and the investigator has developed. Through this network, thousands of MS patients in Germany recently received standardized MRI procedures for disease and therapy monitoring in routine clinical practice, providing hundreds of neurological centers in Germany with regular quantitative information on BVL and lesion activity.

The proposed study has the upside to build on this unique, large network and contribute to better understanding to what extent thalamus volume loss (TVL) appears as an independent driver of disability progression in early MS patients. Once proven and confirmed independently, TVL could serve as a potentially complementary marker of disease activity and a treatment target in future clinical practice, should surrogacy for disability progression be proven. Previous work has provided some important evidence rendering such ambitious goals within sight:

- 1. In the SUNBEAM and RADIANCE phase III trials, MS patients in the OZANIMOD groups showed a significant slowing of cortical gray matter and thalamic volume loss as compared to an active comparator (Cohen et al. 2019; Comi et al. 2019).

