## Outcomes/Endpoint Variables

Primary hypothesis and primary endpoint

The change of MS-related disability during a period of 24 months is inversely associated with the change of thalamus volume during the same period.

MS-related disability will be characterized by the Expanded Disability Status Scale (EDSS). The EDSS will be determined at inclusion (baseline), at 24 months after inclusion, and at additional visits at time intervals approx. every 6 months in between. The annual change of EDSS during the 24-month time period will be computed by linear regression of EDSS versus time including all visits. The change of thalamus volume will be determined in consecutive high-resolution T1w-MRI using a deep-learning based method developed and validated by JDX (Opfer et al. 2020). TVL will be calculated for each pair of two consecutive MRI scans using an advanced and validated method from Opfer et al (2020). The primary endpoint is the Pearson coefficient of the correlation between the annual change of EDSS and the annual change of the thalamus volume.

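### Nothing keeps volumetry results from the site evaluators who score EDSS, so rater knowledge of atrophy could contribute to the primary correlation; the size of any such effect is unknown

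*Protocol*

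**What the plan says.** Under Outcomes/Endpoint Variables the protocol states: "The primary endpoint is the Pearson coefficient of the correlation between the annual change of EDSS and the annual change of the thalamus volume". The EDSS side comes from the sites. The synopsis (Data Collection Methods) says "Evaluators at the study sites record clinical data and information required for the study after each patient visit", and Study procedures adds "The study will require the same evaluator to perform all EDSS assessments for an individual patient when possible". The rating safeguards are that constant evaluator, a standard documentation template, and training: "EDSS raters will be certified using the Neurostatus Standardized Examination and Assessment", with recertification every two years.

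On the flow of imaging results, the synopsis says "The investigator can rely on an established infrastructure and a dense network of study centers and affiliated radiology centers". Data entry and coding procedures describes that network as "providing hundreds of neurological centers in Germany with regular quantitative information on brain volume loss and lesion activity". According to the Study Rationale, in this network "accurate measurement and usage of whole brain volume loss (BVL) has become a" de facto standard of care.

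On timing, the footnote to the Time and events schedule reads: "There is no strict requirement that brain MRI examination shall fall within +/- 3 months of the assessment of clinical scores". Length of follow-up says that the visits V1 to V3 serve mainly to order the MRI.

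The section Bias/confounding and effect modification deals with treatment imbalance and pseudo-atrophy. It does not mention what the EDSS evaluator knows about the MRI. The protocol says neither that thalamic results of study patients go back to sites nor that they are withheld.

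**The concern.** EDSS rests on a neurological examination, and borderline functional-system findings leave room for judgement. An evaluator who knows that a patient's brain volume is falling faster than normal may resolve such findings upward at later visits. The EDSS slope and volume loss would then move together for a reason unrelated to disease, and in the direction the study hopes to show. Certification and a constant evaluator reduce random rating error, but they do not remove expectation. A constant evaluator also carries knowledge of earlier reports forward.

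What is at stake is how a small positive result is read. The expected correlation is 0.15, so even a modest artefact would be a sizeable share of it. The same route could reach S2, which sets disability change in months 24 to 36 against earlier thalamus volume change. What the evaluator has seen before scoring is a matter of conduct. It has to be settled in the protocol before enrolment and cannot be restored by a later analysis plan.

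**Working it through.** **1. The planned effect and the plan's own figure.** Inputs from Power/Sample Size: r = 0.15, type I error 0.05, type II error 0.20. Fisher z, two-sided: n = ((1.960 + 0.842)/atanh(0.15))² + 3 = 346.6, so 347, which matches the protocol. (One-sided gives 274, which does not match.) The smallest significant |r| is tanh(1.960/√(n − 3)): 0.105 at n = 347, and 0.094 at the 433 patients that the attrition table expects at month 24.

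**2. How much knowledge of BVL says about TVL.** The network reports named in the protocol concern BVL and lesions, not TVL. The expected groups under Secondary objectives (section 4) are about 50% both normal, 25% pathological TVL only, 25% both pathological, and 0% pathological BVL only. So P(TVL pathological) = 0.50, P(BVL pathological) = 0.25, P(both) = 0.25, and

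phi = (0.25 − 0.50 × 0.25)/√(0.50 × 0.50 × 0.25 × 0.75) = 0.125/0.2165 = 0.58.

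Knowing BVL is therefore partial knowledge of TVL.

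**3. Which visits matter.** With EDSS at 0, 0.5, 1, 1.5 and 2 years, the centred times are −1, −0.5, 0, 0.5 and 1, and their squares sum to 2.5. A shift of b points at months 18 and 24 changes the slope by b × (0.5 + 1.0)/2.5 = 0.6b per year. Month 12 has weight zero. With b = 0.25 the slope shift is 0.15 per year, all of it from months 18 and 24, when a baseline-to-month-12 report may already be known.

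**4. Illustration only.** None of the following is in the protocol: true correlation zero, TVL treated as pathological yes/no, every patient with pathological BVL shifted by b at months 18 and 24, and an SD of the annual EDSS slope of 0.3 to 0.7. With s = √(0.25 × 0.75) = 0.433,

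induced |r| = 0.577 × 0.6b × s/√(SD² + (0.6b × s)²).

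| b (points) | SD 0.3 | SD 0.5 | SD 0.7 |
|---|---|---|---|
| 0.10 | 0.05 | 0.03 | 0.02 |
| 0.25 | 0.12 | 0.07 | 0.05 |
| 0.50 | 0.23 | 0.15 | 0.11 |

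For orientation, an induced |r| of 0.05 would raise the two-sided rejection rate at n = 347 from 5% to 15%, and one of 0.10 would raise it to 46%. These figures show sensitivity. They do not estimate what will happen.

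**5. What adjustment would do.** In this illustration the rating shift is constant within each BVL stratum, so within a stratum it has no covariance with TVL. Stratifying on or adjusting for BVL status takes the induced association to zero.

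**6. What a release order would do.** If the month-12 report is opened only after the month-12 EDSS, the full 0.15 per year remains. If it is held until after the month-18 EDSS, 0.25 × 1.0/2.5 = 0.10 per year remains. For the BVL route, then, a release order removes between none and one third of the illustrated shift.

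**The case against.** The strongest reply is that the key link is inferred. The sentence on network reports describes established practice in general. It names BVL and lesions, and it mentions neither TVL nor PENTAGON evaluators. The only study-specific image flow described runs from radiology to the investigator. This stands, and a reader who infers that the protocol feeds thalamic results to its raters goes beyond the text. The silence still matters, because the sites order the scans for therapy monitoring and nothing stops results from coming back to them.

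A reader might also infer that no analysis could remove the bias. That is not supported: for knowledge of BVL, step 5 shows that adjustment does remove it. S1 already tests the association only in patients with stable parenchymal volume, which largely closes this route for S1. Only knowledge of TVL itself would escape such adjustment, and the protocol does not say that TVL is reported.

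Nor do the documents support saying that both sides of the correlation are equally exposed. TVL is computed by an algorithm, and the scan exclusion under Bias/confounding follows a rule on the timing of a therapy switch. Scan quality control without EDSS data is therefore a precaution.

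Because the visits serve mainly to order the MRI, the EDSS will often precede that period's scan. This is true, but the footnote on timing means that the order is not guaranteed.

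Finally, therapy changes prompted by MRI belong to a non-interventional design. They are recorded, and treatment is a listed covariate. They are not rater bias.

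**Conclusion.** The gap is real. A judgement-based outcome is scored by site evaluators in a network that routinely returns atrophy results, and the protocol neither keeps volumetry from them nor fixes the order of scoring and results. Rater knowledge of atrophy could contribute to the primary correlation in the hypothesised direction. The protocol's own figures support two parts of this: the phi of 0.58 between pathological BVL and pathological TVL, and the small planned correlation of 0.15, with about 0.105 already significant at n = 347.

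The size is unknown. The range of 0.02 to 0.23 for an induced |r| rests wholly on assumed rating shifts, assumed slope SDs and evaluators who all know the result. It should not be read as a predicted bias, and no false-positive rate should be attached to the study on its account. The conclusion also assumes that volumetry reaches evaluators, which is likely in this network but not stated. This is a low-cost improvement worth making before enrolment. It does not invalidate the design, and the sample size of 347 is unaffected.

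**What to change.** Add to the protocol:

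1. Study-derived TVL and deep gray matter results are not reported to sites until the patient's last study EDSS. Routine radiology reading and existing routine BVL reports continue.
2. Each EDSS is scored and dated before the evaluator opens the volumetry from that period's MRI.
3. Scan quality control and scan exclusion are carried out without access to EDSS data.
4. At each EDSS, the CRF records whether the evaluator had already seen a volumetry report for the patient. A sensitivity analysis repeats the primary correlation adjusted for BVL (or within normal BVL) and by this item.

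Item 4 is needed because routine BVL reports remain known at months 18 and 24, the visits that carry the whole illustrated shift. Items 1 and 2 alone would leave most of that route open.

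The cost is one CRF item and a somewhat later release of volumetry reports, with no extra visit, procedure or assessor. Masking stays partial. Adjusting for BVL may also remove some true association between thalamus loss and disability, so it belongs in a sensitivity analysis and should not replace the primary analysis.
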